 - As more research is done, an uncertain or negative result could change to something else. And if we learn of a change, or of a reason that may impact their wanting to continue study participation that we will contact them.
3. If the results are positive or uncertain, the test is confirmed in the hospital lab, and this confirmation allows the results to become part of their child's medical record.
4. Once information is placed in the medical record it cannot be removed. So, if they call after this has occurred, we can stop research but cannot remove the information from their child's medical record. Usually give an example of what happens if they withdraw before and after the 6-month time point of receiving results.
5. When discussing medically actionable items:
 - Remind them that since this GS test is not new, there are some changes that we know cause health issues and that these issues are typically something that happens as an adult. Therefore, the professional genetics organization, has made it optional for parents to learn this information. Regardless of what they decide, it will not change the care they receive or what happens to study participation (i.e. We still follow until their child is 18, phone interviews still occur).
 - Because these conditions usually happen as an adult, finding them may mean that they, the child's other parent or other family members may need to be tested. The study does not cover these tests; the cost is billed to them/their insurance.
 - Offer to let parent read this section of the consent on the screen

6. Ask if they will sign consent form 2.

Assent form 1 and 2:

1. Intro yourself again to the child
2. Tell them you're going to talk to them about the study, but first you would like to know if they have any questions about what they overheard you telling their parent
3. Tell them their parent will get a copy of what we talk about and that a phone number is on it. So, if they have a question later, they can ask their parent to call and their question(s) will be answered.
4. That although you may like too, you can't change anything that the Dr. (state their name) wants to happen.
5. Tell them that like in school they have to study to learn things, that we are doing this study to learn if a test, will help doctors learn why they and other kids have to come see them.
6. That we are seeing 850 kids and that we ask half the kids if we can look at their medical records until they are 18, and the other half of the kids we ask if we can look at their medical records and that they give a little extra blood (like 1-2 teaspoons). Giving this extra blood just means adding small tubes to the ones the doctor wants. They will not get stuck another time.
7. Us looking at their records does not mean they have to come back to see us, it just means work for us to do.
8. Ask if it's okay for you to flip the coin to see which group they are in
9. Pause and tell them which group they are in
10. Tell them the test is looking to see if there is a change in their genes that is the reason for why they came to clinic today.
11. The test will either say "yes" we see a change that is the reason, "no" we don't see a change that is the reason, or "we see a change" but don't know what it means. That we all have changes, and some cause people to come to the doctor and others don't.

Blood Draw:

- On side pocket of red bag are gloves and extra blood supplies.
- While family is waiting for blood draw to occur (or sooner if possible), do the following:
 - Label the tubes
 - In upper right- hand corner of the white provider signed MGL form, place study label and hand write date and time of blood draw
 - After tubes are obtained, complete the BSP form
 - After blood draw is done, walk them back to the area outside of phlebotomy and give them directions on how to exit the hospital. Then prepare the biohazard bags as below. If they valet parked, they go to either the hospital staff member at the front of the phlebotomy section or the information desk and they contact the valet service.
 - In one biohazard bag place the MGL form and the blood tube with the smaller amount of blood and send this bag to the CORE lab via the shoot system. Number for the core lab is 30. There is long delay between when select enter, for the tube to be sent and it actually goes. Stay there until the tube is gone and the screen is as it was before you sent the tube.
 - In the other biohazard bag, place the tube with the higher amount of blood and the completed BSP form into the red biohazard bag and take it to the BSP.
 - If needed help the parent hold/calm the child during blood draw.

In the phlebotomy area, take the family to the desk area closest to where you enter the phlebotomy section. The parent gives the child's name and DOB and the name of the doctor who saw them. They do not need to take a number or see someone in the glass office area, because they have already checked into clinic.

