Role ¹	Blinding Status	Tasks (Not exhaustive, may vary by site)
Study Coordinator	Unblinded to participant randomizations as they occur	Eligibility and Selection, Enrollment, Mailing 2 & 3, Consents/Assents, Biospecimen Collection
PI/Clinical Project Director	Unblinded throughout	Oversee study design, resolve implementation issues
Research Assistant	Blinded to Intervention 1 randomization through clinic visit Unblinded to intervention 2	Mailing 1, Pre- and Post-Visit Surveys, Audio Recordings, RoR Parent Mailings, Biospecimen Collection
Data Analyst/Programmer	Unblinded throughout	Generates enrollment reports, ensures clean data
Lab Staff	Blinded to identifying information on participants	Analyzes biospecimens and records results
Genetic Counselor	Blinded to Intervention 1 randomization through clinic visit Unblinded to intervention 2	Post-RoR Provider surveys, Consents/Assents (if necessary)
Clinicians	Blinded to Intervention 1 randomization through clinic visit Unblinded to intervention 2	Post-Visit and Post-RoR Provider Surveys, PhenoTips, Return results

¹ The same person can hold multiple different roles across sites and therefore have different blinding statuses at each.

ENROLLMENT OVERVIEW

This section of the protocol describes the participant enrollment process for NCGENES 2 up to the 1st clinic visit.

Participant Referral

The set of all potential participants in the NCGENES 2 study is comprised of children (less than 16 years of age) referred for a disorder with unknown but suspected genetic etiology, who are scheduled in the Pediatric Neurology or Pediatric Genetics and Metabolism clinics at the University of North Carolina at Chapel Hill, the Pediatric Genetics clinic at East Carolina University in Greenville, NC, or the Pediatric Genetics and Metabolism clinic at Mission Health in Asheville, NC. Each participant will have an initial status of “Referred” in the NCGENES 2 Tracking System. Referred participants’ scheduling and demographic information will either be populated nightly from the UNC Carolina Data Warehouse for Health (CDW)¹ or will be entered manually into the study’s tracking system following review of scheduling information in the Electronic Medical Record (EMR). Study staff will use this tracking system throughout the enrollment and data collection process, starting with manual entry or auto-population of patient scheduling data and the identification of eligible participants.²

Participant Eligibility

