This section of the protocol outlines the procedures that should be followed before, during and after the clinic visit. The Visit 1 protocol includes information for preparing for a clinical visit, confirming participant clinic date, documentation collection, conducting pre-visit surveys, facilitating audio recording of clinic visit, conducting post-visit surveys, invitation to and consenting for intervention/randomization #2 (genomic sequencing), and distribution of incentives. This section also covers special topics for clinic visit 1 which include participant distress and no-show protocols and information for physician surveys and entry of PhenoTips information.

Most of the tasks in visit 1 are conducted by the study RA and Study Coordinator. The RA greets the families and handles all tasks up to the post-visit survey after which the RA transitions the participants to the SC.

Preparation for Visit 1

Detailed task lists for the study coordinator and research assistant can be found in [Appendix IV](#) (see page 191). To prepare for a clinic visit, both the Study Coordinator and RA should ensure that all electronic devices needed for clinic are fully charged, including audio recorders, tablets and iPads.

Additionally, study staff should download movies/cartoon content on the iPad/tablet for child participants weekly. Prior to the clinic visit, the Study Coordinator compiles a hard copy folder for each participant and, if necessary, books a consultation room in the clinic where randomization, payment, child gift/snack distribution and genomic sequencing-related consenting will take place.

Compiling the Participant Folder

The Participant Folder principally contains a complete set of Visit 1 documents (used if electronic system fails). **No indication of study randomization status should be included in or on the participant's folder.** This folder is then given to the RA so that it can be brought to the clinic for use. The participant folder should be compiled as follows:

1. Label a Manila Folder with the participant's NCG ID.
2. With the folder open flat and label positioned in the top right corner, place a sticky note on the left side of the folder with the parent and child's name, child's age, and provider's name.
3. On the right side of the folder, clip the following items:
 - a. Envelope with parent participant cash compensation (\$70)
 - b. Blood draw bag with the following items:
 - i. Study ID Labels (5)

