- Chargers for all 3 electronic devices listed above
- Extra stylus
- Snacks
- Hard copy receipt book for parent compensation in the event electronic tablet version fails
- Pens (for completion of forms if tracking fails)
- Post-it notes
- Children's gifts – age appropriate

To make sure the audio recorder is charged:

1. Turn on the recorder by sliding the POWER/HOLD switch toward “POWER.”
2. Check that the battery has three bars.
3. If the battery doesn’t have three bars, charge the battery.

To charge the battery:

1. Connect the USB cable to the USB port of a computer.
2. While the recorder is turned off, connect the USB cable to the bottom of the recorder.
3. Press the PLAY/OK button to start charging, which takes about three hours.
4. Charging is complete when the battery says “F”.

Visit 1 Procedures

Arrival to Visit 1

The RA, blinded to the participant's randomization statuses (pre-visit preparation and genomic sequencing), will coordinate with anyone who will be assisting with the clinic/research visit (e.g., study coordinator, student volunteer, and/or other research and clinical staff). Prior to leaving for the research appointment, if the RA does not see the SC in the NCGENES office, they should inform the SC by text or phone that they are on their way to clinic or have arrived at clinic. The RA should arrive at the clinic at least 15 - 20 minutes prior to the research visit. Upon clinic arrival, the RA should begin looking for the patient and their parent. About 20 - 30 minutes before the research appointment, the SC will check EPIC or Cerner to learn if the patient has arrived and will continue to monitor EPIC/Cerner until the patient arrives. By text, the SC will inform the RA of the patient's status per EPIC at the time of the initial EPIC review and periodically until the patient's arrival.

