The dialog box is titled "Intake Completion Information - Completion Information". It contains the following questions:

1. Does the participant have their completed Intake Survey?
 Yes No
2. Did the participant complete the survey and leave it at home?
 Yes No
- 2A. Is the participant completing the survey in the clinic or at home?
 In clinic At home

At the bottom right are two buttons: "Save" and "Save & exit".

[figure not shown]
iii. Indicate whether the participant will complete the survey at the clinic or at home. If at home, provide the parent with a prepaid envelope as prompted. In any case, click the blue “Finish & Finalize” button to complete the task.

Baseline Intake

The Baseline Intake will in most cases be completed by the parent on paper before they arrive to Visit 1. After collecting the paper copy, a study staff member, usually the RA, will enter the survey information into the tracking system after the fact. In cases where the parent has not yet completed the Intake and time allows, the parent may fill out the survey on the tablet in the clinic before their visit. This step-by-step guide covers both scenarios.

Completion in the Tracking System

1. First copy the “Baseline Intake” code from the individual participant’s page (shown below).

The screenshot shows the NCGENES 2 tracking system interface. At the top, there are navigation links: NCGENES 2 (UNC), Participants, Calendar, Mailings, Documents, and a user profile for [name]. Below the navigation, there is a search bar with the placeholder 'Name: [REDACTED]'. The main content area is titled 'Participant Login Form' and contains the instruction 'Enter the survey code you were given in the form below.' A text input field is labeled 'Survey Code' and contains the value 'XQ2K2W'. To the right of the input field are 'Cancel' and 'Submit' buttons. Below this section, there is a 'Example Questions' button. At the bottom, there is a table with three rows of survey data:

	Date	Description	Status	Action
2	07/12/2019	Intro Letter and Brochure (2460)	Completed	See data
4	07/19/2019	Enrollment Call (2461)	Completed	See data
5	07/12/2019	Visit 1 Appointment Packet - without Pre Visit Prep (2462)	Completed	See data

On the right side of the table, there is a box with the identifier 'WRVN03' and the text 'Post-Visit 1 Parent Questionnaire ver 3'. Below this box is another box with the identifier 'XQ2K2W' and the text 'Baseline Intake v2'.

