S. The doctor was definite about what the problem is.	Very strongly disagree	Strongly disagree	Moderately disagree	Neither agree nor disagree	Moderately agree	Strongly agree	Very strongly agree
T. The doctor was positive about when the problem would settle.	Very strongly disagree	Strongly disagree	Moderately disagree	Neither agree nor disagree	Moderately agree	Strongly agree	Very strongly agree
U. I felt encouraged to ask questions.	Very strongly disagree	Strongly disagree	Moderately disagree	Neither agree nor disagree	Moderately agree	Strongly agree	Very strongly agree

Page 2 of 10

Back Next

Save Save & exit

[REDACTED] - Post-Clinic Visit 1 Survey - Your Clinic Visit Continued View Data

3. How prepared did you feel to take part in the appointment today? (Check one)

Not at all prepared
 A little bit prepared
 Very prepared
 Extremely prepared

4. Did you ask the questions you would have liked to ask in the appointment today? (Check one)

No, I did not have any questions
 No, I did not ask the questions I wanted to ask
 Yes, I asked some of my questions
 Yes, I asked all of my questions

5. Which of the following statements best describes how you used the Question Prompt List, which we mailed to you before today's visit? (Check one)

I did not receive it in the mail
 I received it in the mail, but I did not read it
 I received it and read it, but I did not mark any questions on it
 I received it, read it, and I marked some questions on it

6. How confident are you that you will be able to follow your child's doctor's recommendations for your child's care? (Check one)

Not at all confident
 A little bit confident
 Very confident
 Extremely confident
 Not applicable

Page 3 of 10

Back Next Save Save & exit

[REDACTED] - Post-Clinic Visit 1 Survey - Your Clinic Visit Recommended View Data

7. Did your child's doctor that you saw today recommend or order any of the following for your child?

A start, stop, or change in medication (not including vitamins)?

Start
Stop
Change (for example, stop taking one medication and start another one; or increase or decrease the dose or frequency)
Not applicable

A start, stop or change to any non-genetic tests for screening, monitoring, or diagnosis (for example, blood test, imaging such as x-ray, MRI, etc.)

Start
Stop
Change (for example, increase or decrease the frequency)
Not applicable

Consult with other doctors or specialists

No
Yes
Stop seeing other doctors or specialists
Not applicable

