13. Open survey on tablet and hand to parent for completion (with or without stylus or touch). Let parent know to hand you the tablet when done. Stay nearby for questions/tablet challenges.
14. Obtain tablet from parent (click finish, if needed)
15. Re-open a patient specific 'task' page and confirm pre-visit 1 parent survey now has a 'completed' status
16. Click on parent permission to audiotape task and read/state that study is trying to learn about parent and physician communication and would like to audiotape the clinic visit and that if the parent consents they will check "yes" and sign
17. Hand the tablet to the parent to indicate "yes" or "no" and sign

¹ SC or unblinded member of the study team will provide RA with the appropriate post-visit survey for each participant.

² If the patient is approached prior to check in, just do a brief introduction and inform them you will speak with them after check-in - do not want to delay check-in process)

³ Tasks 10-18 may be completed after patient has been weighed, etc. by nurse and placed in exam room.

18. When they return tablet to you, type in the parent's name, then sign and date and type your name as witness before clicking "Finish and finalize"
19. Prior to genetic counselor (or physician) entering the room, turn on audio recorder (side bar), then press record and say the recorder number and participant's study ID number¹
20. Set recorder and case on shelf in clinic room out of reach of patient
21. When done, let the genetic counselor or physician (they sit in work room) know that you are finished, and the patient is ready for clinical visit to begin²

(Both the counselor and physician will need to see patient next)
22. Go to waiting area/consultation room and, if possible, enter the paper intake form into the tracking system,³ while monitoring whether the clinician has concluded their visit
23. At the end of the visit, turn off and collect tape recorder and provide post-visit survey (ideally in the exam room, though the post-visit survey can be administered in the waiting/consultation room if needed)
24. Provide the post-visit parent survey as you did pre-visit survey via a new surveys tab, BUT use the appropriate survey code for the post-visit survey on the participant page

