- Review this information to confirm the patient's DOB, MRN#, appointment information, and language spoken is the same as that listed in the tracking system.
- If any of the data is different, revise the tracking system to contain the same information that is listed in EPIC and as necessary add a note in tracking to document any changes.
- Review the patient's medical record information in EPIC to determine if the patient meets study's clinical inclusion criteria.
- Make appropriate selections in the tracking system to indicate the patient's study eligibility, per the above EPIC review.
- For ineligible patients, no further action is needed
- For eligible patients:
 - Ask an RA to send the study introduction letter (SC will serve as their back-up)
 - Make enrollment calls
 - Update tracking system to reflect the outcome of enrollment calls
- For participants that agree to be in the study:
 - Based upon randomization for intervention 1, have an unblinded RA create and mail enrollment packet (SC will serve as their back-up)
 - Add participant to NCGENES calendar
 - For participants attending the genetics & metabolism clinic, make a note in MEDGIS that patient is an NCGENES participant
 - For patients attending the neurology clinic, email [name] to inform her of their participation²
 - Inform RA, student volunteer, and [name] of upcoming clinic dates and times
 - Make reminder calls and update tracking system to reflect call outcomes
- 1 to 2 days before clinic:
 - Provide RA attending clinic with the appropriate post-clinic visit survey for each participant
 - Check SC clinic bag to ensure it contains all needed supplies and age appropriate participant gifts (generally there are 2 gift choices per participant)

¹ All actions before and during clinic are in the production version of the NCGENES tracking system.

² The email should contain the patient name, MRN#, appointment date & time, and provider name (generally, SC sends [name] an email twice a month regarding study participants)

To do in clinic:

During initial meeting:

- Introduce yourself
 - Typically, parents are told on the phone that they will meet with [name] or another member of the team in clinic. If you spoke with the family on the phone, introduce yourself accordingly
 - If not, tell the parent you work with [name]

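### Appendix IV has unblinded staff choose a post-visit survey for the research assistant who must stay blind to Intervention 1, and Question 5 of the only version shown is untrue for control parents

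*Protocol*

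**What the plan says.** **Blinding of the RA.** The table under NCGENES 2 Clinical Study Roles lists the RA as "Blinded to Intervention 1 randomization through clinic visit" and gives the RA the pre- and post-visit surveys. Arrival to Visit 1 describes the RA as "blinded to the participant's randomization statuses (pre-visit preparation and genomic sequencing"). Compiling the Participant Folder lists the parent post-visit survey among the paper contents, sends the folder to the RA, and orders in bold: "No indication of study randomization status should be included in or on" the folder.

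**Supply of the survey.** In Appendix IV, footnote 1 of the RA list is attached to creating the participant folders. It says that the "SC or unblinded member of the study team will provide RA with the appropriate post-visit survey for each participant". The Study Coordinator (SC) list repeats the step among tasks due one to two days before clinic: "Provide RA attending clinic with the appropriate post-clinic visit survey for each participant".

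**Question 5.** The parent questionnaire reproduced under Post-Visit 1 Parent Questionnaire asks: "Which of the following statements best describes how you used the Question Prompt List, which we mailed to you before" the day's visit. Its first response option is that the list did not arrive. Under Mailing 2, only parents randomized to pre-visit preparation are sent the list.

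**What control parents know.** The enrollment-call randomization script tells them that they were selected not to receive the pre-visit guide.

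**The concern.** If only unblinded staff can pick the right survey, the natural inference is that there is a right survey for each arm. A paper form chosen that way and placed in the RA's folder would then be a sign of allocation, in conflict with the folder rule and the role table. The RA would have it before meeting the family, so before administering the pre-visit survey as well as the post-visit one.

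If there is only one form, nothing leaks to the RA through it, but control parents read a false statement about an aid partway through the instrument. The control script names the guide and not the list, so the item may be the first a control parent hears of the list by name.

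Intervention 1 aims to help parents get more from the visit, and this survey holds parents' own reports of that visit. The protocol chose to blind the person who administers it. A step that may defeat the blinding, or an item that prompts one arm differently, works against that choice.

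**Working it through.** The protocol states no figure on this point, so the check compares passages and counts questions.

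**1. Does the survey differ by arm?**
- For: the footnote makes being unblinded the qualification for supplying the form. The post-visit survey is not described as age-specific, unlike the intake survey, so age does not explain the selection. Under Mailing 4, the two-week survey for sequenced families does come in versions with and without pre-visit preparation.
- Against: the example task page under Individual Participant Page is for a prep-arm participant. The one under Baseline Intake is for a participant whose packet task is shown as without prep. Both carry the same version 3 label for the post-visit parent questionnaire.
- Result: not settled by the text. Arm-specific forms are an inference.

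**2. If versions differ, where is the exposure?** The electronic survey opens from a participant-specific code, and Tracking System Roles describes a role blinded until Visit 1 is completed. Arm-specific content could therefore be served without the RA seeing it. The exposed route is the paper form handed over.

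**3. If there is one version, how much follows Question 5?**
- By numbered question: 4 before, 15 after; 15/19 = 79% of the others.
- Items before: Q1 (22) + Q2 (21) + Q3 (1) + Q4 (1) = 45.
- Items after: Q6 (1) + Q7 (8) + Q8–13 (6) + Q14 (3) + Q15 (14) + Q16 (5) + Q17 (5) + Q18 (3) + Q19 (7) + Q20 (1) = 53.
- Share after: 53/(45 + 53) = 53/98 = 54%.

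Current emotions, the 21-item rating of the doctor, preparedness and question-asking come before Question 5. Confidence in following recommendations, topics discussed, confidence in explaining tests and the provider ratings come after it.

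**4. Do the two branches cover every case?** No. Arm-specific electronic versions routed by code, with no arm-specific paper form, would avoid both problems. The protocol does not say that this is the arrangement, and the Appendix IV step would then have no purpose.

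**The case against.** The strongest reply is that no sentence says the survey differs by arm, that the shared version label suggests it does not, and that the folder copies are a backup for system failure. On that view the footnote is loose drafting. This stands as a reason not to claim that the RA is in fact unblinded. It does not explain why two task lists call for a per-participant selection, and it leaves Question 5 untrue for control parents.

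It can also be said that RA blinding is fragile anyway: the notes on document collection foresee a parent trying to hand the list to the RA. That is true, but an occasional disclosure by a parent differs from a step applied to every participant.

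A reader might infer several stronger things that the documents do not support:
- *Control parents learn their arm from Question 5.* They were told on the enrollment call, and the item offers a did-not-receive answer.
- *The RA who mails packets breaks the role table.* Appendix IV tells the SC to "have an unblinded RA create and mail enrollment packet", but the Randomization 1 section allows another unblinded staff member to mail it. The SC list refers separately to the RA attending clinic, and the role table says that its tasks are not exhaustive and may vary by site.
- *The task pages show the RA the arm.* An example page does list "Visit 1 Appointment Packet - without Pre Visit Prep (2462"), but the login behind it is not stated, and the page under Individual Participant Page displays the allocation labels themselves. The manual does not show what a blinded login displays.
- *Most outcomes are affected.* By item the majority after Question 5 is bare, and several later items are factual or report the doctor's view.

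**Conclusion.** The point holds as an inconsistency to be resolved, with a cheap improvement to the instrument. The rule that the RA stays blind and the folder carries no sign of allocation does not fit with having unblinded staff select the RA's survey form. Either that form can reveal the arm before Visit 1, or the step is unnecessary and the common form misinforms control parents ahead of 15 of 20 questions (53 of 98 items). Code-routed versions would escape both, but the protocol does not describe them.

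The size of any bias is unknown. It is tempting to assume a shift in the control arm and set it against a standard error, but no figure in the protocol supports a particular shift. Both parent surveys are self-completed: the RA reads the instructions and stays available for questions, so the RA's knowledge could affect administration and assistance, not scoring. The control-arm effect, if any, is a prompt about an aid by parents who already know they were not assigned the guide. The conclusion assumes that the reproduced form, whose arm is not identified, is the one in use.

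**What to change.** 1. Use one post-visit parent survey for both arms. Make it the last question, with conditional wording, for example *If you received a Question Prompt List, how did you use it?*, and keep the did-not-receive option. The Visit 1 reminder call already refers to the educational materials in this conditional way.
2. Delete the step in both Appendix IV lists in which unblinded staff select a survey for the RA. If arm-specific forms are kept, say so, and deliver them by survey code or in a sealed envelope that the RA does not open.
3. Confirm, and state under Tracking System Roles, that the blinded role does not display packet task names that reveal the arm.

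The cost is one reordered and reworded item, two deleted lines and a check of one system role. The downside is small: moving the item partway through enrollment creates a new survey version, which must be flagged in the data so that responses before and after the change can be told apart.
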